Endpoints	 Principal Investigator's assessment of improvement at 12 weeks post-final treatment (Physician's Global Assessment) 		
Safety Endpoint	Incidence and severity of adverse events during the study period, including subject pain level at follow ups		
Subject Population	Female and male subjects, age 25 to 65 years , Fitzpatrick Skin Type Classification I-VI		
Planned Schedule	First subject enrolled: August 2017		
	Last subject last visit: April 2018		

1 PURPOSE

The purpose of this investigation is to evaluate the safety and efficacy of the truSculpt radiofrequency (RF) device for wrinkle reduction and improvement of skin quality.

2 BACKGROUND INFORMATION

Non-invasive treatment options to improve one's appearance are in high demand by patients wanting to avoid surgical intervention. Due to this demand, patients have a variety of options for non-invasive wrinkle-reduction treatment, from laser and light-based treatments to devices that utilize ultrasound and radiofrequency. By delivering energy into the skin in the form of light, ultrasound or radio waves, thereby causing heat generation in the sub layers, these treatment modalities can be used to improve wrinkles and skin laxity [1-24].

Ultrasound and radiofrequency (RF) devices are increasingly utilized for non-invasive tissue tightening due to the ability of these technologies to penetrate the dermis at greater depths, as compared to light-based devices [25-27]. When collagen is heated sufficiently, intramolecular bonds sensitive to heat are broken and the collagen fibril transforms form a highly-organized structure to a random, gel-like state. Immediate collagen contraction occurs as a result of unwinding of the triple helix structure and the residual tension of the heat-resistant intermolecular bonds [30]. The effect of collagen denaturation from tissue heating is dependent on a number of factors, including maximum temperature reached, exposure time, concentration and orientation of the collagen fibers, and the hydration level of the tissue [30]. Many studies have examined histology of post-treatment skin biopsy samples, which demonstrated increased collagen deposition in the weeks to months following device treatments that cause thermal-induced wound healing. In addition, histology samples have demonstrated collagen fibers aligned in a horizontal orientation parallel to the plane of the epidermis. Some studies have demonstrated dermal and epidermal thickening [31]. Uniform volumetric heating of the epidermal, dermal and sub-dermal layers of the skin results in a primary effect of immediate collagen contraction and a secondary effect of fibroblast proliferation and the production of new collagen and elastic over time as a result of inflammation and the wound healing response. [22, 27-29].

RF, which is the most studied device in the non-ablative category, uses electrical current rather than light energy. Unlike light energy, radio waves can penetrate deeper depending on the frequency of operation. RF can be used with all Fitzpatrick skin types without jeopardizing epidermal integrity [33].

RF devices generate heat in the form of thermal energy as a result of electrical current delivered to the tissue. There is a natural resistance to the movement of electrons within the RF field when electrical current is applied [25]. This resistance will dictate the amount of thermal energy generated within the tissue according to Ohm's Law, which states the amount of energy generated is dependent on the electrical current, the tissue impedance and the time of application. Ohm's Law is expressed as an equation, where *I* is the amount of current (in Amps), *Z* is the tissue impedance (in Ohms) and *t* is the time current is applied (in seconds) [25, 30, 32]:

Energy (Joules) = $I^2 x Z x t$

RF may be delivered in three different ways: 1) Monopolar when energy is applied as current between a single electrode tip and a grounding plate. 2) Bipolar when energy is applied between two points on the

tip of a probe. 3) Unipolar when energy is delivered as the emission of electromagnetic radiation (EMR) rather than current and no grounding pad is necessary. This could be achieved by capacitive, inductive or resonant electrical coupling with the tissue.

3 STUDY OBJECTIVES

The objectives of this study are to evaluate the efficacy and safety of treatment with the Cutera truSculpt RF device for wrinkle reduction and improvement in skin quality with handpiece sizes 9cm², 12cm², and 16cm².

4 STUDY DESIGN

This is multi-center, pivotal study with approximately 40 subjects, age 25 to 65 years, who desire RF treatment for wrinkle reduction and improvement in skin quality. Subjects will receive RF treatments) and will be followed at) and 12 weeks) post-

treatment.

4.1 STUDY ENDPOINTS

4.1.1 Efficacy Endpoints

	Efficacy Endpoints
٠	Principal Investigator's assessment of improvement at 12 weeks post-final treatment (Physician's
	Global Assessment)
•	Efficacy Endpoints Principal Investigator's assessment of improvement at 12 weeks post-final treatment (Physician's Global Assessment)

4.2 Study Duration

Subjects enrolled in this trial will be asked to participate for approximately six to seven months and will complete up to five visits: one screening visit, **RF** treatment visits, **follow-up** visits follow-up visits at 12 weeks

The screening and first RF treatment may be combined into one visit provided that the informed consent process has been completed (see Section 6) and *the subject has signed the IRB-approved Informed Consent Form prior to the commencement of any study related procedures and device treatments.* If the subject does not receive the first study treatment on the same day as screening, the subject must complete their first treatment within 7 days of their screening visit date.

4.3 Study Assessments

4.3.1 Effectiveness Assessment

4.3.1.2 Physician's Global Assessment of Improvement

Principal Investigators will be asked to rate the degree of improvement of the treated area at 12 weeks post-treatment as compared to the subject's baseline photos using the Physician's Global Assessment of Improvement Scale:

- 4 = Very Significant Improvement 3 = Significant Improvement (
- 2 = Moderate Improvement
- 1 = Mild Improvement

4.3.1.5 Treatment-related Discomfort

Subjects will be asked after each procedure (2 total treatments) to rate the average amount of discomfort experienced during RF treatment using the Pain Rating Scale found in Appendix 3.

4.3.2 Safety Assessments

4.3.2.1 Incidence and Severity of Adverse Events:

Following the first RF treatment, adverse device effects (ADEs) will be assessed post-treatment and at each subsequent subject visit using the following scale:

1= mild: requires minimal or no treatment and does not interfere with the Subject's daily activities.

2= moderate: may cause some interference with functioning.

3= severe: interrupts Subject's usual daily activity and may require treatment.

4.4 Photographs

Standardized digital photographs will be taken of each subject's face and submental region. Photographs will be taken at baseline, prior to all RF treatments, and at each follow-up visit. Photographs will be obtained from at least three angles: 1) with the subject facing forward, 2) 45° to the right, and 3) 45° to the left. Photographs will be taken in the same windowless room equipped with adequate lighting. The room lighting, camera positioning and subject positioning should be consistent for all study visit photographs. Digital camera settings should remain the same for all photographs and the highest resolution settings should be utilized.

4.5 Study Discontinuation

The study sponsor has the right to terminate this study at any time. Reasons for terminating the study may include, but are not limited to, unsatisfactory subject enrollment or the incidence or severity of adverse events in this study, or other studies with the study device, indicates a potential health hazard to subjects.

4.6 Investigator Selection

Investigators will be invited to participate in the study based on their medical specialty, experience conducting clinical research studies and experience in the use of energy based devices for aesthetic indications. The site's access to potential study subjects and ability to cooperate with study requirements will also be considered.

5 STUDY POPULATION

5.1 Study Subject Recruitment and Selection

Up to 40 male or female subjects, ages 25 to 65, with Fitzpatrick Skin Type I-VI who desire RF treatment for wrinkle reduction. Subjects will be recruited to participate from those patients who present themselves to the site requesting treatment, or from those patients who respond to advertisement. Only subjects who meet all Inclusion and Exclusion Criteria and provide written informed consent will be enrolled into the study.

Each subject will be evaluated by the Investigator to assess his/her suitability for entry into the study according to the following inclusion and exclusion criteria.

5.1.1 Inclusion Criteria

To be included in the study, subjects must *meet all* of the following Inclusion Criteria:

1.	Must be able to understand and provide written informed consent and release of health information
2.	Male or Female, 25 to 65 years of age (inclusive)
3.	Fitzpatrick Skin Type I – VI (Appendix 4)
4.	Has visible wrinkles or skin laxity in the treatment area
5.	On the Fitzpatrick Classification Wrinkle Classification System subject has a pre- treatment score of 4-9 (inclusive) (Appendix 5)
6.	No use of tobacco products for at least 6 months and willing to refrain from use for the duration of the study
7.	Subject must agree to not undergo any other cosmetic procedure(s) area, or start
	topical retinol products in the treatment area during the study period
8.	Subject must be willing to adhere to the follow-up schedule and study instructions
9.	Subject must be willing to adhere to the same diet and/or exercise routine throughout
	the study, and agree to maintain the same weight throughout the study, within 10% of
	baseline weight measurement
10.	Willing to have digital photographs taken of the treatment area and agree to use of
	photographs for presentations, educational, and/or marketing purposes
11.	For female subjects: not pregnant or lactating and is either post-menopausal, surgically
	sterilized, or using a medically acceptable form of birth control at least 3 months prior to
	enrollment and during the entire course of the study, and no plans to become pregnant

5.1.2 Exclusion Criteria

Subjects will be excluded from the study if they *meet any* of the following Exclusion Criteria:

1.	Participation in a clinical trial of a drug or another device in the target area within 3
	months of study participation, or during the study.
2.	Any type of prior cosmetic treatment to the target area within 12 months of study
	participation e.g., radiofrequency, cryolipolysis, deoxycholate injection, or light-based
	treatments
3.	Prior injection of botulinum toxin, collagen, hyaluronic acid filler, or other dermal filler,
	and medium-depth to deep chemical peels, to the treatment area within 6 months of
	study participation
4.	History of systemic steroid use within 3 months; history of topical steroid use in the
	target area within 2 months
5.	History of systemic retinoid (isotretinoin) and therapeutic dose of Vitamin A within 6
	months of study participation
6.	Has a pacemaker, internal defibrillator, implantable cardioverter-defibrillator, nerve
	stimulator implant, cochlear implant or any other electronically, magnetically or
	mechanically activated implant

7.	Has metal implant(s) within the body that are local to the treatment area, such as surgical clips, plates and screws (metal tooth fillings or crowns will not exclude subject participation), or has , artificial heart valves or artificial joints
8.	Clinically significant concurrent illness, such as diabetes mellitus, cardiovascular disease, peripheral vascular disease or pertinent neurological disorders that in the opinion of the Investigator will confound participation in the study
9.	Diagnosed or documented immune system disorders
10.	History of any disease or condition that could impair wound healing
11.	History of diseases stimulated by heat, such as recurrent herpes zoster in the treatment
	area, unless treatment is conducted following a prophylactic regimen
12.	History of keloid formation, hypertrophic scarring or abnormal/delayed wound healing
13.	Infection, dermatitis, rash or other skin abnormality in the target area
14.	Currently undergoing systemic chemotherapy or radiation treatment for cancer, or history of treatment in the target area within 3 months of study participation
15.	Anticipated or planned need for surgery or hospitalization during the duration of the study
16.	Pregnant, nursing, or planning a pregnancy during the trial; or is a woman of child bearing potential but is not willing to use an acceptable method of contraception as determined by the Investigator
17.	As per the Investigator's discretion, any physical or psychological condition which might make it unsafe for the subject to participate in this study

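### Do the 12-month and 6-month washouts in exclusion criteria 2 and 3 leave the eligibility of some subjects undecided?

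*Combined protocol and SAP*

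**What the plan says.** Three parts of section 5.1.2 (Exclusion Criteria) in the combined protocol and SAP matter here.

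- **Criterion 2** covers "Any type of prior cosmetic treatment to the target area within 12 months of study" entry. Its examples are introduced as illustrations: "participation e.g., radiofrequency, cryolipolysis, deoxycholate injection, or light-based" treatments.
- **Criterion 3** begins "Prior injection of botulinum toxin, collagen, hyaluronic acid filler, or other dermal filler" and continues "and medium-depth to deep chemical peels, to the treatment area within 6 months of" study entry.
- **The rule that joins the criteria** is in the lead-in: "Subjects will be excluded from the study if they *meet any* of the following Exclusion Criteria".

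Neither criterion refers to the other, and criterion 2 makes no exception for the treatments named in criterion 3. One criterion speaks of the target area and the other of the treatment area. The available text does not define these as different regions, so they are taken here to be the same. Section 5.1 adds that only subjects who satisfy the full set of inclusion and exclusion criteria may be enrolled.

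**The concern.** Toxin, fillers and deeper peels are cosmetic treatments on any ordinary reading. Criterion 2 claims to cover every type, and because its list is only illustrative, leaving these items off does not remove them. One of its examples, deoxycholate, is itself an injection, so the criterion cannot be confined to energy devices. A reader who then meets a 6-month window for toxin, fillers and peels may take it as a deliberate exception to the 12-month rule. Otherwise, why write it?

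If some sites read it as an exception and others did not, they would enrol different populations. A subject accepted on the exception reading would be an eligibility deviation on the literal one. The study is multicenter and uncontrolled, so no comparator arm would absorb a residual effect of earlier treatment on the same area. With about 40 subjects, a few extra or missing responders could matter to a test of the response rate against 50%.

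**Working it through.** No figure in the plan depends on this point, so the main check is to set the two criteria side by side for a subject who had toxin, filler or a medium-depth to deep peel in the area.

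| Time since treatment | Criterion 2 (12 months, any type) | Criterion 3 (6 months, listed types) | Result when any one criterion excludes |
|---|---|---|---|
| Up to 6 months | Excludes | Excludes | Excluded |
| Over 6, up to 12 months | Excludes | Silent | Excluded |
| Over 12 months | Silent | Silent | Not excluded on this ground |

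The two criteria differ only in the middle row, and there the combining rule gives a single answer. Criterion 3 can add exclusions but cannot cancel one made by criterion 2. For these treatments it therefore has no effect of its own: everyone it excludes is already excluded by criterion 2.

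**How many subjects?** The documents do not give the share of candidates treated 6 to 12 months before entry. If one assumes 10% to 30%, multiplying by the 39 to be enrolled gives 0.10 × 39 = 3.9 and 0.30 × 39 = 11.7, or about 4 to 12 subjects. That product is not valid for the plan as written. The share describes people who come for screening, whereas 39 counts people already enrolled, and the literal rule enrols none from this window.

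**How sensitive is the test?** Section 9.1 gives a 50% reference rate, an assumed true rate of 76%, 35 subjects and 80% power. The available text shows no significance level, so two-sided 0.05 is an assumption. By exact binomial with n = 35 and p = 0.5, doubling the upper tail:

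- 23 responders: 2 × 0.0448 = 0.090
- 24 responders: 2 × 0.0205 = 0.041

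One subject separates failure from success, but that is so at the cut-off of any binomial test and says nothing about this pair of criteria. Nor is 24 clearly the plan's own boundary. At a true rate of 76%, the chance of at least 24 responders is 88.8% and of at least 25 is 80.0%. Only the second matches the stated power under an exact test. One subject is 1/35 = 2.9 percentage points at 35 subjects, or 1/39 = 2.6 at 39.

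**Which direction of bias?** The Physician's Global Assessment (section 4.3.1.2) compares 12 weeks after treatment with the subject's own baseline photographs, and baseline comes after any earlier treatment. A stable residual effect is present at both times and cancels. Only an effect that changes during the study could matter. A benefit that fades would count against the device, and one still developing would count in its favor. The documents give nothing from which to size either. Inclusion criterion 7 separately has subjects agree to no other cosmetic procedures during the study.

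**The case for a change.** The best case for a change is that a separate criterion with its own window is rarely written to do nothing. The sponsor may well have meant a shorter washout for toxin, fillers and peels, with criterion 2 for everything else. A general rule followed by a specific one is a familiar drafting pattern, and a site could reasonably let the specific rule govern. Subjects are recruited from people who request treatment or answer advertisements, so earlier cosmetic treatment is a plausible screening question. One added phrase would settle the matter.

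Much of this stands. The intent is unclear, and a site that treated criterion 3 as an exception would enrol differently from one that applied the list as worded. The documents do not, however, show that any site did so, and the exception reading has to override the lead-in to the list. A sensitivity analysis without subjects from the 6 to 12 month window would presuppose that such subjects were enrolled, although the plan as written keeps them out.

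**Conclusion.** The overlap is a drafting redundancy and does not call for a change to the plan. Read as written, section 5.1.2 gives one answer for every subject: toxin, filler or a medium-depth to deep peel in the area within 12 months excludes. Applying it literally yields a sound, somewhat stricter population. No bias, loss of power, wrong number or safety cost has been shown, and no additional analysis is warranted.

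This rests on two assumptions: that the target area and the treatment area are the same region, and that sites apply the combining rule as stated. If sites did not, the effect would be some inconsistency in eligibility whose size and direction cannot be worked out from the documents. The sponsor may reconcile the wording of the two criteria as housekeeping. Which window was intended is the sponsor's to say, and this review takes no view on it.

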5.2 Subject Numbering

Each site will be assigned an ID number by the sponsor, and each consented (enrolled) subject will be assigned a subject ID number, comprised of a sequential number assigned for each subject, and the subject's initials. The subject's initials will be comprised of the first letter of the first and last name (example: Site ID/Subject ID/Subject's Initials; 01-01MH).

5.3 Subject Discontinuation Criteria

If possible, every subject should remain in the study until completion of the required follow-up period. However, participation in this study is completely voluntary and a subject can choose to withdraw from the study at any time. In addition, a subject can be discontinued for any of the following reasons: the Principal Investigator decides that continuing in the study would not be in the subject's best interest, a subject is noncompliant with the protocol, a subject has a serious reaction to the treatment, or the study is stopped. In addition, subjects may be discontinued from the study if s/he develops any of the exclusion criteria during the study period. A subject will be considered lost to follow-up only after three unsuccessful, documented attempts to contact the subject have been made. Withdrawn subjects will not be replaced.

Confidential and Proprietary

All potential AEs and ADEs will be evaluated and must be recorded in the subject's medical chart and in the study case report forms. AEs and ADEs will be monitored and tracked from the time of the first RF treatment.

At each contact with the subject, the Investigator will seek information on AEs by specific questioning and, as appropriate, by examination. AEs may be observed by the Investigator and/or clinical research staff, elicited from the subject and/or family member or volunteered by the subject. All observed and volunteered adverse signs and symptoms (both expected and unexpected), regardless of severity or frequency, will be recorded in the (medical chart and CRFs). Included in the description should be the nature of the sign or symptom, the date of onset, date of resolution (duration), the severity, whether the event was expected or unexpected (anticipated or unanticipated), the relationship to study treatment or other therapy, the action taken (if any), and the outcome.

All SAEs and UADEs must be reported according to Cutera and IRB requirements.

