7.3 Follow-up of AEs and ADEs

All reported AEs and ADEs should be followed until resolution or until the subject's participation in the study ends. Resolutions of such events are to be documented on the appropriate CRF pages. All AEs and ADEs that result in permanent discontinuation from this clinical trial, whether serious or not, will also be reported on the Subject Non-Completion of Study Form.

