9.2 Analysis Sets

The efficacy analysis set will include all enrolled subjects who complete one RF treatment session using the study device.

The safety analysis set will include all subjects enrolled in the study who start the RF treatment session using the study device.

Missing data will not be imputed for efficacy or safety endpoints.

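### Section 5.3 permits study-level discontinuation of treated subjects without separating it from stopping RF treatment and without asking for the 12-week assessment, so obtainable outcomes can be lost.

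*Combined protocol and SAP*

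**What the plan says.** Section 5.3 opens with a retention aim: "If possible, every subject should remain in the study until completion of the required follow-up period". It then lists reasons for which a subject can be discontinued. One is the Principal Investigator's judgement of the subject's best interest. The list continues: "a subject is noncompliant with the protocol, a subject has a serious reaction to the treatment", and it ends with the stopping of the study itself. It adds that "subjects may be discontinued from the study if s/he develops any of the exclusion criteria during the study period". On replacement it says: "Withdrawn subjects will not be replaced".

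The only kind of discontinuation in the legible text is discontinuation from the study. Section 7.3 fits that reading: adverse events "should be followed until resolution or until the subject's participation in the study ends".

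The legible efficacy endpoint in section 4.1.1 is the "Principal Investigator's assessment of improvement at 12 weeks post-final treatment". Section 4.3.1.2 has the Principal Investigator make that rating against the baseline photographs. Section 4.4 schedules photographs at every follow-up visit.

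Section 9.2 defines the analysis population: "The efficacy analysis set will include all enrolled subjects who complete one RF treatment session using the study device". The same section rules out imputation of missing values.

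**The concern.** Sections 5.3 and 9.2 pull in different directions. Section 9.2 treats a subject with one completed session as belonging to the efficacy analysis, whatever happens next. Section 5.3 allows that subject's participation to end before the single time point at which the legible endpoint is rated. The subject then sits in the efficacy set with no outcome, no imputed value and no replacement.

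Several permitted reasons need not prevent a photograph and a rating. As examples of my own, a subject who resumes tobacco, whose weight moves outside the 10% band in the inclusion criteria, or who takes a course of systemic steroids could usually still attend at 12 weeks.

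Lost precision is the smaller issue. The study is open-label and uncontrolled, and the Principal Investigator both can decide that a subject should not continue and rates the Physician's Global Assessment. Removal can therefore be related to how the subject is responding, without any intent to select. If non-responders leave more often than responders, the observed response rate is too high, and no analysis rule can fully replace a rating that was never taken.

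**Working it through.** **Inputs.** Section 9.1 gives a reference rate of 50%, an assumed response rate of 76%, 35 subjects for 80% power, a dropout allowance of up to 10%, and 39 enrolled. Alpha and the definition of the tested endpoint are not legible. I assume an exact one-sample binomial test and take one-sided 0.025 as the main case.

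**The plan's own figures.**
- Enrolment: 35 / 0.90 = 38.9, rounded up to 39. This reproduces. The allowance is 39 − 35 = 4 subjects for all causes.
- Power is P(X ≥ r | n = 35, p = 0.76), where r is the smallest count with P(X ≥ r | n = 35, p = 0.50) ≤ alpha.

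| One-sided alpha | r | Attained alpha | Power |
|---|---|---|---|
| 0.05 | 23 | 0.045 | 94.3% |
| 0.025 | 24 | 0.020 | 88.8% |
| 0.01 | 25 | 0.0083 | 80.0% |

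The stated 80% reproduces at one-sided 0.01. At 0.025, 35 subjects are more than enough.

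**If losses are unrelated to outcome.** At one-sided 0.025, power is 88.8% with 4 of 39 lost, 85.3% with 6 and 81.0% with 8. At one-sided 0.01 it is 80.0%, 74.7% and 68.2%. Under the main assumption, lost power is not the problem.

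**If losses are related to outcome.** Take the extreme case: all 4 allowed dropouts are investigator removals and all are non-responders. Compare the analysis of assessed subjects with the result had the 4 been rated, using P(X ≥ x | n, 0.50).

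| Responders | Assessed only (n = 35) | All treated (n = 39) |
|---|---|---|
| 24 | 68.6%, p = 0.020 | 61.5%, p = 0.100 |
| 25 | 71.4%, p = 0.0083 | 64.1%, p = 0.054 |
| 27 | 77.1%, p = 0.0009 | 69.2%, p = 0.012 |

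The first row is the lowest passing count at 0.025 and the second is the lowest at 0.01; in each the conclusion reverses. The third row is near the planned rate (0.76 × 35 = 26.6). It still passes at 0.025, though 27 is the lowest passing count for n = 39, and it would not pass at 0.01.

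**False-positive rate in the same extreme case.** Suppose the true rate among all 39 is 50% and k non-responders are removed. The rate among those left is 0.50 × 39 / (39 − k).
- k = 2: 52.7%, and the chance of passing at nominal 0.025 is about 4.9%.
- k = 4: 55.7%, about 8.5%.
- k = 6: 59.1%, about 14.4%.
- k = 8: 62.9%, about 23.1%.

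For k = 4, fixing the removals as exactly four of the non-responders instead gives P(X ≥ 24 | n = 39, 0.50) = 10.0%, so the answer is roughly 8.5% to 10% depending on the model.

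**The case against.** **The rule is permissive.** Section 5.3 says what can or may be done, after asking that subjects remain where possible. A reader might infer that it removes subjects automatically, or that any reaction is enough. The documents do not support either: loss of the visit is allowed, not required, and the text says a serious reaction. This limits the claim but does not close the gap. Discretion is what makes outcome-related removal possible, and the retention sentence does not tell a site to obtain the rating once it has acted.

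**Deviations already have a home.** Section 11.3.2 records missed visit windows and incorrect procedures on a form and does not say that they end participation. This stands, and part of the fix is therefore clarification.

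**The tested endpoint is not visible.** The endpoint compared with 50% in section 9.1 is blacked out, and section 9.3 lists the Physician's Global Assessment under descriptive analysis. A reader might infer that the arithmetic concerns that assessment, or that 12 weeks is the only time point for every efficacy endpoint. Neither can be confirmed. The overlap of rater and decision-maker is established only for the Physician's Global Assessment.

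**The illustration is a worst case.** It takes the lowest passing count and assigns the whole allowance to removed non-responders. The 10% also covers voluntary withdrawal and loss to follow-up, which better wording would not recover. This stands.

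**Text is missing.** Most of section 6 and the study schedule are absent, and section 7.3 mentions a non-completion form. An early-termination assessment may exist there.

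**Conclusion.** The concern holds in a limited form. As legible, section 5.3 permits study-level discontinuation of treated subjects for reasons that need not prevent a 12-week assessment. It does not separate this from stopping treatment, and it does not ask for the assessment afterwards. With the efficacy set and no-imputation rule of section 9.2, that allows avoidable 12-week gaps which may depend on outcome.

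The likely size is unknown. A near-threshold result could reverse under the extreme assumption, while a result near the planned rate would survive at one-sided 0.025. These figures rest on an assumed test, an assumed alpha and an assumed link between removal and non-response. A reader might take them as evidence that the trial's conclusion is at risk as planned; they show only what the wording leaves open. The change is worth making because it is cheap and because an outcome that was not collected cannot be recovered. If the removed section 6 text already requires an early-termination or 12-week assessment, only a cross-reference in 5.3 is needed.

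**What to change.** In section 5.3, define two separate states: no further RF treatment, and withdrawn from the study. Ask every subject who completed at least one session and has not withdrawn consent to complete the planned follow-up photographs and ratings, unless the investigator sees a best-interest reason against attending. Record noncompliance or a later exclusion criterion as a deviation under section 11.3.2, so that it does not by itself end assessment. Leave the clinical criteria for stopping treatment and the best-interest judgement unchanged.

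The cost is protocol wording; the visits are already planned for these subjects. The downside is that some ratings will come from partly treated or noncompliant subjects, so the observed response rate may be slightly lower. That is consistent with the population section 9.2 already defines.
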